9.7.2. Secondary objectives

• To determine the total health burden of non-RSV-associated RTI with a suspicion of involvement of the lower respiratory tract.

Incidence rates will be calculated as the number of non-RSV-associated RTI with a suspicion of involvement of the lower respiratory tract over the number of children-years observations, overall and by subgroups.

Descriptive statistics of the different types of healthcare utilization will be provided (proportions, duration, etc.) among non-RSV-associated RTI with a suspicion of involvement of the lower respiratory tract, overall and by subgroups.

• To evaluate the association between RSV-associated LRTI, RSV-associated severe LRTI and RSV neutralizing antibodies in the baseline cord blood samples collected from subjects, at birth.

The impact of the level of RSV neutralizing antibodies in the baseline cord blood samples on the risk of having a RSV-associated LRTI and RSV-associated severe LRTI will be assessed through a statistical model.

Incidence rates will be calculated overall and by level of antibodies in the cord blood sample, as the number RSV-associated LRTI/severe LRTI as classified by the case definition and severity scale over the number of children-years observations.

• To determine the prevalence of RSV infection, at 2, 4, 6, 12, 18 and 24 months in a randomly selected sub-cohort of subjects by assessing antibodies in serum.

The primary analysis will be based on ATP sub-cohort for this objective.

Infection by RSV will be assessed (with 95% CI) by time point as the proportion of samples with a positive score of antibody titer after adjusting for baseline antibody results over the total number of samples.

Scores will be determined based on the measured antibody titer *vs*. the expected antibody level at the time of sampling based on the individual baseline (cord blood) value and the average, modelled decay rate.

• To assess the between calendar year variability in the incidence rates of RSVassociated LRTI.

Incidences rates will be calculated as the number of RSV-associated LRTI/severe LRTI as classified by the case definition and severity scale, over the number of children-years observations, in the subgroups of subjects recruited from months 1-6 and from months 13-18.

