9.7.3. Tertiary Objectives

• To explore the association of co-infections with the incidence of RSV-associated LRTI and/or severe LRTI (as determined by the LRTI case definition and severity scale) using xTAGTM RVP Fast assay.

For each of the other respiratory viruses, incidence rates will be calculated as the number of RSV-associated LRTI/severe LRTI cases associated co-infected with the virus over the number of children-years observations.

• To explore the association of RSV and other respiratory viruses with the incidence of LRTI and/or severe LRTI (as determined by the LRTI case definition and severity scale) using xTAGTM RVP Fast assay.

For each of the respiratory viruses, incidence rates will be calculated as the number of LRTI/severe LRTI cases associated with the virus over the number of children-years observations.

• To explore the association of RSV viral load with the incidence of RSVassociated RTI, LRTI and/or severe LRTI (as determined by the LRTI case definition and severity scale).

Descriptive analyses (mean, median, min, max) of viral load assessed by the RSV RTqPCR of RSV RTI, RSV LRTI and severe LRTI cases will be tabulated.

• To explore the impact of changes to the symptoms and threshold levels of symptoms in the LRTI case definition and severity scale.

Frequency tables will summarize the proportion of RSV-associated LRTI/ severe LRTI cases associated with a list of symptoms and clinical parameters, overall and by age categories.

This will help us to determine potential areas of improvement of the LRTI case definition and severity scale. Incidence rates of RSV-associated LRTI/severe LRTI will be calculated for any proposal of modification of the LRTI case definition and severity scale.

• To explore the impact of variations in cord-blood sample collection variables on the stability of test results.

The measured maternal antibody levels will be assessed versus variability in sample collection variables. This involves assessment versus various continuous and categorical variables and an overall comparison between samples as classified 'according to recommended procedure' and 'not according to recommended procedure'.

The measured maternal antibody levels by duration of the processing step and overall process duration will be analysed graphically and by log-linear regression.

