3.2. Secondary objectives

In a cohort of infants followed-up from birth up to 2 years of age;

- To determine the total health burden of non-RSV-associated RTI with a suspicion of involvement of the lower respiratory tract.
- To evaluate the association between RSV-associated LRTI, RSV-associated severe LRTI and RSV neutralizing antibodies in the baseline cord blood samples collected from subjects, at birth.
- To determine the prevalence of RSV infection, at 2, 4, 6, 12, 18 and 24 months in a randomly selected sub-cohort of subjects by assessing antibodies in serum.
- To assess the between calendar year variability in the incidence rates of RSV-associated LRTI.

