6.10. Analysis of other viruses and RSV infection

6.10.1. Analysis of tertiary objective: incidence of other respiratory viruses as cause of LRTI and severe LRTI

The number and percentage of cases for each respiratory virus identified for all WHO LRTI and WHO severe LRTI. For each respiratory virus infection, number and percentage will be summarized by single or co-infection status.

The number and percentage of cases associated with each of the other respiratory viruses, with at least one other a respiratory virus, 1, 2, or more than 2 additional viruses, will be described for WHO LRTI and WHO severe LRTI.

The percentage will be computed using the number of cases (associated with each of the other respiratory viruses, with at least one other a respiratory virus, 1, 2, or more than 2 additional viruses) divided by the total number of case for a given endpoint.

This analysis will be performed at less than 3 month, between 3 - 5 month, 6 - 11 month, and 12 - 23 months and by country.

Statistical Analysis Plan Amendment 1 Final

Other respiratory viruses include Influenza A (subtypes H1 and H3); Influenza B; Parainfluenza virus type 1, 2, 3, and 4; Human Metapneumovirus; Rhinovirus/Enterovirus; Adenovirus; Bocavirus and Coronavirus - 229E, OC43, NL63, HKU1. The analyses will be performed for each viral type and aggregated viral types, for example, viral type of parainfluenza will combine parainfluenza virus type 1, 2, 3 and 4.

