7. ANALYSIS INTERPRETATION

Analyses will be descriptive with the aim to characterise overall occurrences, patterns and potential differences between groups in the endpoints related to the objectives. No hypothesis testing will be performed.

The tertiary objective 'To explore the impact of changes to the symptoms and threshold levels of symptoms in the LRTI case definition and severity scale' will be assessed if we detect potential areas of improvement of the LRTI case definition and severity scale, such as clearly under or overestimated incidence rates of LRTI/ severe LRTI compared to the rates in the literature or a lack of discriminative power between severe and non-severe cases. This decision will not be taken on specific pre-defined thresholds.

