9. CHANGES FROM PLANNED ANALYSES

- Due to the number of subjects with examination visit but without surveillance visit:
 - RSV LRTI endpoints computed using data from examination visit were added to the endpoint RSV-associated RTI with a suspicion of involvement of the lower respiratory tract definition computed using data from surveillance visit
 - The delay between LRTI identification and swab sample is not considered in the case definition
 - The subgroup analysis by collection time of swabs (72 hours/48 hours from the start date of the case (date of the call), 72 hours/48 hours from the reported onset of symptoms) has been removed
- In protocol it is suggested to analyse by country and then pool by hemisphere and region. Pooling across such diverse settings is not developing strong messages about RSV incidence and therefore we limit our subgroup analysis to by country. Where the protocol described overall incidence we have preferred to only do pooled incidence across countries by year of life. This aids meaningful interpretation and minimises tables.
- In the analysis of the key healthcare utilization and health outcomes: the hospitalization status, intensive care unit attendance, clinical diagnosis of bronchiolitis or pneumonia, death has been replaced by: outpatient visit, emergency Room visit, inpatient Admission (non intensive care), innpatient Admission (intensive care), no consultation other than site clinic and other.
- In the analysis of the performance of case definition, the key health outcome does not include intensive care unit attendance, clinical diagnosis of bronchiolitis or pneumonia and death. Instead, hospitalization status according to WHO, GSK, Nokes, and exploratory case definition will be used for the analysis.
- The incidence rates of RSV-associated LRTI/severe LRTI as classified by the GSK and Nokes case definition are not computed.
- Incidence rate of all cause RTI provided instead of per protocol non-RSV associated RTIs as RSV RTIs are subset of all cause RTI. Hence analysis of all cause RTIs is more relevant and conventional in epidemiological studies.
- Descriptive statistics of the different types of healthcare utilization will not be provided among non-RSV-associated RTI with a suspicion of involvement of the lower respiratory tract, overall and by subgroups.

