11.2.1.3. All cause RTI with suspicion of involvement of lower respiratory tract

The status RTI with suspicion of involvement of LRTI will be assessed using data from surveillance visit and data from examination visit.

200150 (EPI-RSV-005 BOD)

Statistical Analysis Plan Amendment 1 Final

The subject will be considered positive for RTI with suspicion of involvement of LRTI:

- positive for RTI at surveillance visit AND positive for a suspicion of involvement of LRTI at surveillance visit
- AND/OR when the subject has attended an examination visit (whatever LRTI final assessment)

The subject will be defined as positive for RTI at surveillance visit when he is presenting one or more of the following items:

- Did or does the child cough? (fields [SRV_RTI.CATEGORY] ="Cough" and [SRV_RTI.QUEST_YN]=Y")
- And/or did or doe s the child have runny nose? (fields [SRV_RTI.CATEGORY] ="Runny nose" and [SRV_RTI.QUEST_YN]=Y")
- And/or did or doe s the child have a blocked nose? (fields [SRV_RTI.CATEGORY] ="Blocked nose" and [SRV_RTI.QUEST_YN]=Y")

The subject will be considered positive for a suspicion of involvement of LRTI when he subject has attended an examination visit (whatever LRTI final assessment) or when he has one or several of the following items is reported in interview during the surveillance visit:

- Did or does the child make noises like wheezing or grunting when breathing? (fields [SRV_RTI.CATEGORY] ="Wheezing or grunting" and [SRV_RTI.QUEST_YN]=Y")
- And/or did or does the child breathe faster than normal? (fields [SRV_RTI.CATEGORY] ="Breathe faster" and [SRV_RTI.QUEST_YN]=Y")
- And/or did or does the child flare his/ her nostrils when breathing? (fields [SRV_RTI.CATEGORY] ="Flare Nostrils" and [SRV_RTI.QUEST_YN]=Y")
- And/or did or does the child use his/ her muscles in chest and neck when breathing? (fields [SRV_RTI.CATEGORY] ="Use muscles" and [SRV_RTI.QUEST_YN]=Y")
- And/or was or is the child short of breath? (fields [SRV_RTI.CATEGORY] ="Short of breath" and [SRV_RTI.QUEST_YN]=Y")

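### The SAP keeps the non-RSV burden objective but produces neither an incidence nor a healthcare-use result for non-RSV illness, and it turns virus-specific incidence into case percentages without listing that change

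*SAP*

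**What the plan says.** **Objective.** SAP 3.2 repeats the protocol's secondary objective: "To determine the total health burden of non-RSV-associated RTI with a suspicion of involvement of the lower respiratory tract". SAP 3.1 defines health burden as incidence together with associated healthcare use.

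**Protocol analysis.** Protocol 9.7.2 plans two outputs. One is a rate, the number of "non-RSV-associated RTI with a suspicion of involvement of the lower respiratory tract over the number of children-years observations". The other is: "Descriptive statistics of the different types of healthcare utilization will be provided (proportions, duration, etc.) among non-RSV-associated RTI".

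**SAP analysis.** Section 6.6.2 and Template 15 give first-episode rates of all-cause illness only, although Template 15 sits under the heading of the non-RSV objective. Section 9 gives the reason: "Incidence rate of all cause RTI provided instead of per protocol non-RSV associated RTIs as RSV RTIs are subset of all cause RTI". It also removes healthcare use for non-RSV episodes. Section 6.7 and Templates 18 and 19 cover WHO RSV LRTI and WHO RSV severe LRTI only.

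**Other viruses.** For each virus, protocol 9.7.3 says "incidence rates will be calculated as the number of LRTI/severe LRTI cases associated with the virus over the number of children-years observations", and it plans the same form of rate for RSV co-infections. SAP 6.10.1 gives instead: "The number and percentage of cases for each respiratory virus identified for all WHO LRTI and WHO severe LRTI". Its percentage uses the number of cases as denominator. Section 6.10.2 and Templates 53 to 55 do the same, with no person-time. SAP 3.3 keeps the word incidence in the objectives, and section 9 has no entry for this change.

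**The concern.** A secondary objective that remains in the plan has no output of its own. The reason offered, that RSV illness is contained in all-cause illness, is exactly why the all-cause rate cannot measure the non-RSV part. A reader of the report would meet Template 15 under the non-RSV heading and could take all-cause rates for non-RSV rates. For healthcare use there is not even an all-cause table.

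For the other viruses, a percentage of cases depends on how often every other cause occurs. It cannot be compared across countries or ages as a rate per child-year can. Because section 9 is silent, a reader of the SAP would not know that planned rates were dropped.

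**Working it through.** The documents state no figure on this point. The text comparison settles what is missing, and the arithmetic below shows only the size of the gap under assumed rates.

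**1. Planned against produced**

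| Output | Protocol | SAP |
|---|---|---|
| Non-RSV incidence | cases over child-years (9.7.2) | all-cause first-episode rate (6.6.2, Template 15); declared |
| Non-RSV healthcare use | descriptive statistics (9.7.2) | none; declared |
| Incidence by virus | cases over child-years (9.7.3) | n and % of cases (6.10.1, Templates 53, 55); not declared |
| RSV co-infection incidence | cases over child-years (9.7.3) | n and % of cases (6.10.2, Templates 53, 54); not declared |

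**2. All-cause rate relative to non-RSV rate**

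With constant hazards and RSV share s of episodes, the ratio is 1/(1 − s). Protocol 1.1.1 quotes s = 11% (day-care RTI) and 58% (hospitalized LRTI). Protocol 1.1.2 quotes up to 80% (infant LRTI). The ratios are 1/0.89 = 1.12, 1/0.42 = 2.38 and 1/0.20 = 5.0.

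**3. Does subtraction recover the non-RSV rate?**

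Protocol 9.3 expects RSV hospitalization rates of 10 to 50 per 1000 child-years and RSV LRTI 8 times as often. That gives 0.08 to 0.40 per child-year, and 20 × 8 = 160 per 1000, or 0.16, as a middle value.

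Under SAP 11.1.1 person-time stops at the first event, so the planned measure is

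rate = [1 − S(2)] / ∫₀² S(t) dt.

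- *Constant, homogeneous, independent hazards.* The rate equals the hazard λ. With RSV 0.16 and s = 58%, all-cause is 0.16/0.58 = 0.276, and 0.276 − 0.160 = 0.116, which is the non-RSV rate. Subtraction is exact.
- *Shared gamma frailty, variance θ.* S(t) = (1 + θλt)^(−1/θ). For θ = 1 the integral is ln(1 + 2λ)/λ. With RSV 0.40 and s = 80% (all-cause λ = 0.50, non-RSV λ = 0.10):
  - all-cause: 0.5000 / (ln 2.0 / 0.50) = 0.3607
  - RSV: 0.4444 / (ln 1.8 / 0.40) = 0.3025
  - non-RSV: 0.1667 / (ln 1.2 / 0.10) = 0.0914
  - difference: 0.3607 − 0.3025 = 0.0582, and 0.0582/0.0914 = 0.64, so 36% too low.
- *Grid.* Over RSV rates 0.08, 0.16 and 0.40, shares 11%, 30%, 58% and 80%, and θ = 0.5 and 1, the difference is 4% to 36% too low.

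**4. Completeness of testing**

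SAP 11.2.1.3 counts a child as all-cause positive if "positive for RTI at surveillance visit AND positive for a suspicion of involvement of LRTI at surveillance visit", and/or if an examination visit was attended. Swabs are taken only at examination visits (protocol 6.5.16). Template 62 provides for contacts where the indicated visit came after more than 6 days or never. For RTI with suspicion, all-cause minus RSV therefore mixes untested with RSV-negative illness. WHO LRTI needs oxygen saturation or respiratory rate measured at an examination visit (SAP 11.2.1.4.1), where a swab is planned, so only the swabs not done (Template 64) remain a problem.

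**5. Percentage against rate**

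A virus found in 20% of LRTI cases means 0.20 × 100 = 20 per 1000 child-years if the LRTI rate is 100, and 0.20 × 500 = 100 if it is 500.

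**6. A definition to reconcile**

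Table 4, as printed, adds to the all-cause definition a condition of confirmed RSV infection or self-referral. Section 11.2.1.3 has no such condition. The two would give different numerators.

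**The case against.** The non-RSV change is open: section 9 states both the all-cause substitution and the loss of healthcare use, and gives a reason for the first. Protocol 9.10 allows analyses to be modified if the report justifies it. The SAP is descriptive throughout ("No hypothesis testing will be performed"), so no inference rests on the choice, and reporting all-cause incidence is legitimate in itself. All of that stands. It explains why all-cause rates are shown, but not why the objective is kept without a result.

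Four stronger readings are tempting, and the documents do not support them.

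- *Non-RSV incidence can never be recovered by subtraction.* On the planned person-time rate it can be, under the idealised conditions in step 3, and for WHO LRTI the testing gap is limited to swabs not done.
- *A gap in proportions affected proves the point.* Proportions do not subtract even in the ideal case, but the SAP plans them only for RSV endpoints (Templates 9, 10 and 35), not for all-cause illness.
- *RSV's share of LRTI will be unknown.* Templates 53 and 55 tabulate RSV-A and RSV-B among WHO LRTI and WHO severe LRTI cases, and Template 53 does so by age and country. The N for all and for RSV-positive cases gives the count not confirmed as RSV, though without person-time and with unswabbed cases included.
- *The virus objective is unanswered.* Counts and percentages by virus are planned, by age and country, and RSV incidence itself is reported under the co-primary objective. The objective is described, but not as incidence.

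**Conclusion.** The point holds in this form. Both components of the retained non-RSV objective, incidence and healthcare use, have no output. The planned per-child-year rates for other viruses and RSV co-infections are replaced by case counts and percentages without an entry in section 9. These conclusions come from the text and need no assumptions.

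The sizes do rest on assumptions. The ratio of 1.12 to 5.0 assumes constant hazards and borrows RSV shares from different settings. The 4% to 36% shortfall assumes shared gamma frailty over two years with complete testing. Neither is a prediction for this cohort. The co-primary RSV results are not affected, but the SAP should be changed so that the secondary objective has a result.

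**What to change.** 1. In Template 15, add first-episode rates for RSV-negative illness (swabbed and RT-qPCR negative): RTI with suspicion, WHO LRTI and WHO severe LRTI. List untested episodes separately.
2. Run Template 18 for RSV-negative RTI with suspicion and RSV-negative WHO LRTI, as far as healthcare use was recorded at examination visits (SAP 11.2.4).
3. In Templates 53 and 54, add virus-positive and RSV co-infected cases per 100 child-years with confidence intervals. Use total follow-up person-time in the age interval, because these tables count all cases while the rule in 11.1.1 stops at the first episode.
4. If the virus rates are not restored, list that change with its reason in section 9.
5. Reconcile the all-cause definition in Table 4 with section 11.2.1.3.

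The cost is one derived RSV-negative/untested flag, one person-time rule and a few extra table rows, using data already collected. The all-cause rates stay.

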5.1.3. Per-protocol Set (PPS)

Note that in order to align to ICH and cDISC terminology the According To Protocol (ATP) cohort as stated in the protocol has been renamed Per-Protocol Set (PPS) respectively.

The PPS will include all subjects meeting all elimination criteria up to the time of their censoring (study termination), either at study completion or prematurely as drop-out (e.g. withdrawn consent, lost-to-follow-up, lack of compliance).

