6.1.4.9. Other

- Age of the subject at time of the LRTI case will be expressed in months and will be computed as the difference between the start date of the LRTI case and the date of birth.
- Age of the subject at time of blood sample collection will be expressed in months and will be computed as the difference between the sample collection date and the date of birth.
- Age of the mother at the time of childbirth will be expressed in years and will be computed as the difference between the birth date of the subject and the birth date of the mother.
- Duration of the study for each subject will be computed as the difference between the date of last contact (i.e., active or passive surveillance contact or the date of the censoring) and the date of enrolment (date when ICF was first signed by the subject's parent[s]/LAR[s]).

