- The risk factor analysis will be done using a Cox regression model and not a Poisson regression model to be consistent with the analysis performed in clinical trials.
- The sensitivity analysis will not be performed on the total enrolled cohort.
- The analysis of the impact of changes to the symptoms and threshold levels of symptoms in the LRTI case definition and severity scale will not be done by age category

200150 (EPI-RSV-005 BOD)

Statistical Analysis Plan Amendment 1 Final

- The date of study conclusion for subjects lost to follow-up will be the date of conclusion given in the CRF and will not be derived according to number of missed visits.
- Only first episode within a given age interval is considered for the computation of incidence. The incidence of event is computed using 3 different calculation methods: incidence rate, proportion affected, and incidence proportion. See section 11.1.1 for detail of calculation
- Sub-group of analysis for birth period outside or within transmission season will not be performed. Instead, the analysis will be based on the first 6 month of subject's life, and will be done considering 2 categories: <= 3 months and > 3 months. The incidence rate of RSV associate LRTI, severe LRTI, and hospitalization will be computed by country.
- Incidence and performance of case definition analysis (measures of agreement) will be performed using exploratory case definitions in anticipation of update to WHO case definitions.
- Analyses of cord blood collection using and not using recommended procedures will not be done. Instead, descriptive statistics for cord blood collection variables and cord blood levels of RSV A and B neutralizing antibodies according to cord blood collection variables will be provided. Additional analyses will be performed to evaluate disease surveillance and protocol procedures and include summary of number and percent of surveillance contacts followed by an exam visit, the duration between surveillance contact and exam visit, and duration between nasal swap and onset of symptoms.

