11. ANNEX 1 STANDARD DATA DERIVATION RULE AND STATISTICAL METHODS

11.1. Statistical Method References

11.1.1. Computation of incidence rates

For each endpoint, the incidence rate (IR, number of episodes/endpoints per 100 personyears) will be calculated by dividing the number of subjects reporting first episode over the follow-up period by the total person-year. A 95% CI will be computed using an exact method for a Poisson variable as described below.

The person-time at risk for an event of interest (e.g. RSV-LRTI) will be calculated as the time between the date of birth and the end of the at-risk period or the earliest of the followings:

200150 (EPI-RSV-005 BOD)

Statistical Analysis Plan Amendment 1 Final

- Date of first diagnosis of event of interest (e.g. first episode of RSV-LRTI);
- Date when child reaches 2 years;
- Date of last contact (lost-to follow-up, defined as no contact by the subject's parent(s)/LAR(s) over the period of 3 planned contacts and/or 2 months and after a final attempt has been made by mail. Once this has been reached, the subject is censored at the time of last contact);
- Date of death.

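### The SAP gives two conflicting end-of-follow-up dates for children lost to follow-up, and the choice can slightly dilute the co-primary incidence rates

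*SAP*

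**What the plan says.** SAP section 9 lists, as a change from the planned analyses, that "The date of study conclusion for subjects lost to follow-up will be the date of conclusion given in the CRF", and adds that it "will not be derived according to number of missed visits". The bullet that follows it concerns incidence and sends the reader elsewhere: "See section 11.1.1 for detail of calculation".

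SAP 11.1.1 computes the rate by "dividing the number of subjects reporting first episode over the follow-up period by the total person-year". Person-time runs from birth to the earliest of the first event, age 2, last contact and death. Its last-contact entry defines loss to follow-up as no contact "over the period of 3 planned contacts and/or 2 months and after a final attempt has been made by mail", and continues: "Once this has been reached, the subject is censored at the time of last contact".

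Other places do not settle the matter:
- SAP 5.1.3 describes follow-up in the per-protocol set as running "up to the time of their censoring (study termination), either at study completion or prematurely as drop-out", which equates censoring with study termination.
- SAP 6.1.4.9 ends each child's study duration at last contact or at the date of censoring.
- Protocol 8.2 uses data up to withdrawal or last contact and leaves the definition of lost to follow-up to the Study Procedures Manual.
- Protocol 6.5.21 requires a Study Conclusion screen to be completed but does not say what its date means.

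**The concern.** Both rules stand in the current SAP and apply to the same children. The derivation that section 9 rejects is the one that 11.1.1 prescribes. Two programmers working from this SAP could produce different person-years for the same data.

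The choice matters because case finding depends on contact: an RSV case needs a surveillance contact or examination visit and a swab. Protocol Appendix E suspends active surveillance only after more than 3 planned contacts and/or more than 2 months without contact, plus a final attempt. If the CRF date is the date on which loss was declared, a gap of roughly 2 to 3 months after last contact is built in. Time in that gap adds to the denominator with little chance of adding to the numerator.

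Person-years are the denominator of the co-primary incidence rates in SAP 6.6.1. The Kaplan-Meier and Cox analyses also need an end date, and their sections give none of their own. Results are reported by country, so unequal loss could distort comparisons between countries. SAP section 9 also drops the sensitivity analysis on the total enrolled cohort, and none on censoring is planned.

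**Working it through.** **The plan's own figure.** Protocol 9.3 assumes about 20% drop-out, and protocol 5.1 gives 2400 enrolled and about 1920 evaluable: 1920 / (1 - 0.20) = 2400, which reproduces. No figure for person-time or for loss to follow-up is stated.

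**Assumptions not in the documents.** All drop-out is loss to follow-up; last contact is uniform over 0-24 months; the CRF date falls a fixed gap g (in years) after last contact, capped at age 2; no events are recorded in the gap; truncation of person-time at first episode is ignored.

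**Denominator under last-contact censoring.** Lost children: 0.20 × 2400 = 480, contributing 1 year each on average. Base = 1920 × 2 + 480 × 1 = 4320 child-years.

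**Added time under the CRF date.** With T, the age at last contact, uniform on (0, 2) years, E[min(g, 2 - T)] = g - g²/4. Extra = 480 × (g - g²/4), and the rate is multiplied by 4320 / (4320 + extra).

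| Gap | Extra child-years | Change in 0-23 month rate | 20 per 1000 becomes |
|---|---|---|---|
| 0 | 0 | 0 | 20.0 |
| 2 months | 76.7 | -1.7% | 19.65 |
| 3 months | 112.5 | -2.5% | 19.49 |
| 6 months | 210 | -4.6% | 19.07 |
| 12 months | 360 | -7.7% | 18.46 |
| CRF date at age 2 for all | 480 | -10.0% | 18.00 |

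At 160 per 1000 (8 times the hospitalization rate, as protocol 9.3 expects for RSV LRTI), a 3-month gap gives 155.9.

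**First year of life.** Half of the losses (240) fall in year 1: base = 2160 + 240 × 0.5 = 2280, extra = 240 × (g - g²/2). The 0-11 month rates fall by 1.6% for 2 months (36.7 extra), 2.3% for 3 months (52.5 extra) and at most 5.0% (120 extra).

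**Less loss.** At a 3-month gap, 10% loss gives -1.2% (56.2 on a base of 4560) and 5% loss gives -0.6% (28.1 on 4680). A country with 20% loss and one with 5% would thus be shifted apart by about 2.5 - 0.6 = 1.9 percentage points.

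**Scale.** Protocol Table 13 gives an exact interval of [13.0; 29.3] around 20 per 1000 overall for the first year of enrollment: 13.0 / 20 = 0.65 and 29.3 / 20 = 1.465, or about -35% to +47%.

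**The case against.** The strongest reply is that 11.1.1 already governs. It ends person-time at the earliest of several dates including last contact, study conclusion is not among them, and section 9 itself points there for the calculation. On that reading a later CRF date never reaches the denominator. This is a fair reading of 11.1.1, but it leaves section 9 rejecting the missed-contact derivation that 11.1.1 uses, and SAP 5.1.3 equating censoring with study termination. The ambiguity stands; proof that the CRF date is used does not.

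A second reply is that 11.1.1 may hold the leftover text: section 9 records deliberate changes, and the protocol's amendment history shows the missed-contact definition being taken out of the protocol. This also has force, so deleting the section 9 bullet is not the obvious remedy.

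A reader might infer more than the documents support:
- **That the CRF rule necessarily adds unobserved time.** No document defines the CRF date. It may equal last contact, and the added time is then zero.
- **That no case could be found after loss.** Protocol Appendix E suspends active surveillance only. A parent may still report, the case is followed up, and active surveillance can restart.
- **That the Cox results are biased downward.** They are hazard ratios. They are affected only if loss differs by covariate, and then in no fixed direction.
- **That lags of 2, 6 and 12 months inflate person-time by 1.9%, 5.6% and 11.1%.** That follows from 0.2 × lag / (0.8 × 24 + 0.2 × 12), which lets time run past age 2, where 11.1.1 stops it. With the cap, inflation is 76.7 / 4320 = 1.8%, 210 / 4320 = 4.9% and 360 / 4320 = 8.3%.
- **That 20% is the loss to follow-up.** It covers drop-out for any reason, with migration as the example, so it gives an upper bound.

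**Conclusion.** The conflict between SAP section 9 and SAP 11.1.1 is real, sits in current text and affects a co-primary denominator. The bias is conditional: it arises only if the CRF conclusion date is later than last contact and is used to end person-time. In that case incidence rates and Kaplan-Meier cumulative probabilities are diluted, and more where loss is greater.

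The only documented trigger for suspending surveillance points to a gap of 2 to 3 months, hence a fall of at most about 1.7% to 2.5% in the 0-23 month rates if all 20% drop-out is loss to follow-up. Longer gaps have no documentary basis and serve only to bound the effect, at 10%. The likely effect is small beside the planned sampling error. It is nevertheless one-directional, does not shrink with sample size, and can differ by country.

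**What to change.** State one rule in both sections: for the incidence, Kaplan-Meier and Cox analyses, person-time ends no later than the earlier of the CRF conclusion date and the last successful surveillance contact or examination visit recorded in the eCRF. The existing stops at first event, age 2 and death remain. Reword the section 9 bullet and the last-contact entry in 11.1.1 to match, and say what the CRF conclusion date represents. Report the distribution of the gap between the two dates by country, so that readers can see whether the choice mattered.

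The cost is SAP wording and one descriptive table. Protocol 6.5.12 already requires scheduled active contacts and every passive contact to be recorded in the eCRF, so no new data are needed.
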